- 3) Measure the time to emergence from anesthesia

METHODS AND PROCEDURES

Study Design: Describe the research design, including a description of any new methodology and its advantage over existing methodologies.

Two-arm randomized placebo-controlled trial.

Procedures: Describe all procedures (sequentially) to which human participants will be subjected. Identify all procedures that are considered experimental and/or procedures performed exclusively for research purposes. Describe the types, frequency and duration of tests, study visits, interviews, questionnaires, etc. Include required screening procedures performed before enrollment and while on study. Please provide in table, list or outline format for ease of review. (describe and attach all instruments)

Note: A clinical research protocol may involve interventions that are strictly experimental or it may involve some aspect of research (e.g., randomization among standard treatments for collection and analysis of routine clinical data for research purposes). It is important for this section to distinguish between interventions that are experimental and/or carried out for research purposes versus those procedures that are considered standard therapy. In addition, routine procedures performed solely for research purposes (e.g., additional diagnostic/follow-up tests) should be identified.

All patients between the ages of 18 and 80 with an ASA of 1-3 who will be undergoing elective thyroidectomy (partial or complete), parathyroidectomy, or ophthalmological surgery requiring intubation will be eligible for this study. Exclusion criteria include patients with a Lean Body Mass < 20 kg, BMI > 45, the presence of pulmonary dysfunction, any allergy to opioids and patients requiring the use of total intravenous anesthesia. The anesthesia provider may also exclude a patient from the study at any point in time if the provider has concerns for the patient's safety including an inability or expected difficulty with ventilation.

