Study coordinators will identify and consent the appropriate patient on the day of surgery. Patient who agree to participate in the study will be randomized to receiving either a placebo or remifentanyl in a syringe that will be blinded to the patient, the clinicians in the room as well as the study coordinator. Once the patient is in the OR, the setup which includes the syringe, the BBraun Perfusor Space syringe pump and extension tubing will be connected the IV tubing at the most proximal port to the patient. The study coordinators will then input the patient's characteristic into the spreadsheet containing the algorithm, set for a goal remifentanyl effect site concentration of 2.1 ng/mL, and program the syringe pump under the guidance and supervision of anesthesia provider in the room. The study pump will be maintained in a "standby" mode until activated as described below. During the induction and maintenance of anesthesia, the provider has full liberty to manage the anesthetic plan.

In approximately the last 5-30 minutes of surgery, as identified by the surgeon, the infusion pump will start infusing as was previously programmed. Patients whose surgery will end less than 5 minutes prior to the start of infusion, or, patients who will be extubated while deeply anesthetized will be excluded from the study and will not receive any of study drug or placebo. At the conclusion of the surgery, the anesthetic gases will be discontinued, any neuromuscular blocking agent reversed, and, when clinically indicated the patient will be extubated and monitored for adequate respiratory effort. The infusion will be terminated either when the patient is extubated, or at 15 minutes after the start of anesthetic washout. Anesthetic washout occurs at the end of surgery when the anesthetic gases are turned off and high flows of oxygen are administered to purge the residual anesthetic from the system and the patient. The anesthesia provider will ensure suitability for transfer to the post-anesthesia care unit at all times as per usual clinical practice. The study period will conclude once the patient is discharged from direct anesthesia care.

The study coordinators will be tasked with documenting:

- 1) The incidence of cough
- 2) If coughing present, the cough will be graded according to the following scoring guidelines:
 - a. 0=no cough
 - b. 1=slight cough, cough without obvious contraction of the abdomen

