With coughing incidence at baseline expected to be approximately 70% and a target incidence of 30%, we would need to recruit 50 patients in order to achieve an alpha or 0.05 and power of 0.9. Accounting for an exclusion of 20% (deep extubation, improper notice, failure to properly connect the system prior to the start of the case, decision by anesthesiologist to exclude patient, etc.), 60 patients would need to be recruited for this study. We will recruit 60 patients for this study.

Risks/Benefits: Describe any potential or known risks. This includes physical, psychological, social, legal or other risks. Estimate the probability that given risk may occur, its severity and potential reversibility. If the study involves a placebo or washout period, the risks related to these must be addressed in both the protocol and consent. Describe the planned procedures for protecting against or minimizing potential risks and assess their likely effectiveness. Where appropriate, discuss plans for ensuring necessary medical or professional intervention in the event of adverse effects to the subjects. Discuss the potential benefits of the research to the subjects and others. Discuss why the risks to the subjects are reasonable in relation to the anticipated benefits to subjects and others. Discuss the importance of the knowledge gained or to be gained as a result of the proposed research and why the risks are reasonable in relation to the knowledge that reasonably may result. If there are no benefits state so.

The only major risk to the patient is transient respiratory depression which may occur in 5-10% of the population. This is expected to cease promptly (within 5 minutes) after cessation of the infusion. As the patient will be monitored at all times by an anesthesia provider, the actual risk to the patient is minimal as either the patient will be assisted by a ventilator, or the patient's ventilation will be assisted by the provider. It must be stressed that assisting respiration and ventilation is one of the principal tasks of an anesthesia provider and the provider is expected to continue to manage the patient's respiration until the patient is adequate for discharge to the post-anesthesia care unit.

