All adverse events and unanticipated problems will be reported to the PI, who will evaluate them for reporting to the IRB. In the event of any significant adverse event or unexpected event, the project will immediately be placed on hold and reviewed by the Anesthesiology QA committee chair. Such events include but are not limited to: significant hemodynamic aberrations such as bradycardia requiring treatment with multiple doses of atropine; significant hypotension requiring norepinephrine infusion; cardiac arrest; and severe sedation postoperatively requiring invasive airway management such as endotracheal intubation.

Withdrawal Procedures: Define the precise criteria for withdrawing subjects from the study. Include a description of study requirements for when a subject withdraws him or herself from the study (if applicable).

Patients whose surgery will end in less than 5 minutes prior to the start infusion, or, patients who will be extubated while deeply anesthetized will be withdrawn from the study and will not receive any of study drug or placebo. Given the nature of the study and because the patient will be anesthetized at the time of the initiation of infusion, a patient will only be able to withdraw him/herself just prior to induction of anesthesia. The anesthesia provider, may, at any time, request withdrawal in order to provide appropriate patient care

Sources of Materials: Identify sources of research material obtained from individually identifiable human subjects in the form of specimens, records or data. Indicate whether the material or data will be obtained specifically for research purposes or whether use will be made of existing specimens, records or data.

The sources of research material in this study will be 1) data obtained from identifiable human subjects specifically for research purposes while they are undergoing surgery in the operating room, and 2) demographic data obtained from subjects' medical records: Height, weight, age, gender, type of surgical procedure, and all data will be logged in a spreadsheet with no identifiable information other than time of events

DRUG AND DEVICE INFORMATION

Investigators are encouraged to consult the UVM Medical Center Investigational Pharmacy Drug Service ([name]) prior to finalizing study drug/substance procedures.

Drug (s) **Not applicable**

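### Minor, cheap improvement: planned deep extubation is screened out only after randomisation, so some of the 60 allocations can go to patients already known to be unanalysable

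*Protocol*

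**What the plan says.** The eligibility criteria appear twice in the protocol, under Procedures and under Inclusion/Exclusion Criteria. Both give limits on lean body mass and BMI, then further exclusions. The Procedures version continues with "the presence of pulmonary dysfunction, any allergy to opioids and patients requiring the use of total intravenous anesthesia". Both versions also let the anesthesia provider exclude a patient at any time over safety concerns. Neither mentions deep extubation.

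Procedures then gives the sequence. Consent is taken on the day of surgery, and "Patient who agree to participate in the study will be randomized to receiving either a placebo or remifentanyl". The syringe and pump are connected in the operating room, the pump is programmed, and it waits in standby. Only in the next paragraph, on starting the infusion near the end of surgery, does the text state that "patients who will be extubated while deeply anesthetized will be excluded from the study and will not receive any of study drug or placebo". Withdrawal Procedures repeats the rule as a withdrawal: "patients who will be extubated while deeply anesthetized will be withdrawn from the study".

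Statistical Considerations budgets for it: "Accounting for an exclusion of 20% (deep extubation, improper notice, failure to properly connect the system prior to the start of the case" and so on, which takes the number from 50 to 60. The total is fixed ("We will recruit 60 patients for this study"), and no replacement of excluded patients is described.

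**The concern.** A planned deep extubation is information about the anesthetic plan, held by the provider. The protocol already screens on one item of that kind, the need for total intravenous anesthesia. It leaves the other until the patient has been randomised and the pump set up. Where the plan is known on the morning of surgery, the allocation is spent on someone who, under the protocol's own rule, will receive neither remifentanil nor placebo. The same holds for a provider who already expects to decline the patient.

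With recruitment capped at 60, each such case means one fewer evaluable patient for the primary Fisher test and one more randomised patient outside the analysis. Both could be reduced by asking a question earlier.

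**Working it through.** **Inputs from the protocol (Statistical Considerations).** Cough incidence 70% on placebo and 30% on remifentanil; alpha 0.05, sidedness not stated; power 0.9; 50 patients needed; 20% exclusion; 60 recruited; Fisher exact test for cough incidence.

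**Assumptions.** 1:1 allocation (the ratio is not stated), so 30 per arm; losses random and independent of arm; two-sided test for the main calculation.

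**1. The plan's own figures.** The pooled normal-approximation formula, with mean proportion 0.5, is

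n per arm = [z(alpha) × √(2 × 0.5 × 0.5) + z(0.90) × √(0.7 × 0.3 + 0.3 × 0.7)]² / (0.7 − 0.3)².

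- One-sided: (1.645 × 0.7071 + 1.2816 × 0.6481)² / 0.16 = 24.8, so 25 per arm and 50 in total. This reproduces the plan's 50.
- Two-sided: (1.960 × 0.7071 + 1.2816 × 0.6481)² / 0.16 = 30.7, so 31 per arm and 62 in total. This does not.

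The step to 60 is 50 × 1.2. Dividing instead gives 50 / 0.8 = 62.5, that is 63.

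**2. What the allowance delivers if fully used.** 60 × 0.8 = 48 evaluable, 2 short of 50. On the one-sided approximation that reproduces 50, power is 90.2% at 50 and 89.0% at 48, a gap of about 1 point. That gap comes from multiplying by 1.2 rather than dividing by 0.8, not from where the deep-extubation rule sits. Losses up to 10/60 = 16.7% leave at least 50.

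**3. What earlier screening could recover.** The number evaluable in each arm is taken as Binomial(30, 1 − loss). Exact two-sided Fisher power for 70% versus 30% is averaged over those numbers. Averaging is preferable to a single n because Fisher power moves unevenly with n (78.2% at 25 per arm, 75.6% at 26).

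| Share of the 20% avoided | Remaining loss | Expected evaluable | Average power | Chance of fewer than 50 evaluable |
|---|---|---|---|---|
| none | 20% | 48 | 76.6% | 67.7% |
| one quarter | 15% | 51 | 78.7% | 28.4% |
| half | 10% | 54 | 80.1% | 3.4% |
| three quarters | 5% | 57 | 82.7% | about 0% |

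The gain over the first row is 0, 2.1, 3.5 and 6.1 points. The protocol does not give the share, so the rows are scenarios, and the first is as admissible as the others.

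**4. Level versus gain.** With no loss at all, two-sided Fisher power at 30 per arm is 83.8%, still below 90%. The low level throughout the table therefore reflects mainly the basis of the 50 and the 1.2 multiplier. Only the differences between rows belong to this point.

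**The case against.** The strongest reply is that the loss was foreseen. Deep extubation is the first reason named in the 20% allowance, and recruitment was raised for it. That stands. A reader might infer that late screening pulls power below plan, but it does not do so by itself; the small remaining shortfall has a different cause (steps 1 and 2).

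Second, the avoidable share may be close to zero. The 20% also covers improper notice and failed connection, which no question before randomisation would detect. Procedures leaves the anesthetic plan to the provider during the case, so some deep extubations are decided only then. This also stands. It is why the range starts at 0, and why not every deep-extubation patient can be called unanalysable from the outset.

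Third, a reader might infer bias from leaving randomised patients out. The documents do not support that: the exclusion comes before any study drug, and the syringe is blinded to patient, clinicians and coordinator, so the decision should not depend on allocation. The cost is precision.

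Fourth, provider exclusion at any time already covers refusals before randomisation on safety grounds. True, but nothing prompts the question at that stage, and a planned deep extubation need not be a safety concern.

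Finally, the requirement that the system be connected before the case starts might seem to conflict with a pump that stays in standby until the last part of surgery. It does not. It agrees with the set-up step in Procedures, and loosening it would permit pump programming during surgery, when the protocol itself lists misprogramming as a risk.

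The narrower point survives: nothing is gained by randomising a patient already known to be headed for exclusion.

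**Conclusion.** The point holds as a minor efficiency improvement. The protocol neither lists planned deep extubation as an exclusion nor asks about it before randomisation, so part of a fixed 60 may be spent on patients known not to be analysable. The benefit of asking first is 0 to about 6 points of power and 0 to 9 more expected evaluable patients (48 rising to at most 57 in the scenarios shown). This rests on 30 per arm, random losses, 70% versus 30% cough, a two-sided Fisher test at 0.05, and an avoidable share of zero to three quarters, which is an assumption. It is not a shown bias, not an internal contradiction, and not the cause of the low absolute power.

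**What to change.** 1. In both eligibility lists (Procedures and Inclusion/Exclusion Criteria), add the exclusion: *deep extubation already planned, as confirmed with the anesthesia provider before randomisation*. At the same time, ask whether the provider already expects to exclude the patient.
2. In Procedures, place randomisation after that check, at the point where the study syringe is requested. The Preparation entry already has the drug kept in the refrigerator until requested for the study, so this appears workable.
3. Keep the existing pre-infusion exclusion and its counterpart in Withdrawal Procedures for decisions made later. The method of extubation remains the provider's choice. Leave the connection-timing wording in Statistical Considerations as it is.

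The cost is a short amendment, one question to the provider on the day of surgery, and slightly more screening to reach 60. Deep extubations decided during surgery will still be lost, so an exclusion allowance remains necessary.

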Many methods have been proposed to avoid coughing during extubation with variable success rates. The most promising method involves using remifentanil, an ultra-short acting opioid, with an advanced medication-delivery system that is not available in the U.S. We have recently demonstrated how to replicate the performance of this system using a standard medication pump and an algorithm that can be run on a spreadsheet or mobile app.

(2) The purpose of this study is to determine whether using remifentanil with our algorithm can in fact decrease or prevent coughing around the time of extubation. For eligible patients we will randomly administer remifentanil or a placebo in their intravenous line at the time that surgery is concluding. An independent observer will then determine whether or not the patient coughed at the end of surgery and qualify the intensity of the cough.

PURPOSE AND OBJECTIVES

Purpose: The importance of the research and the potential knowledge to be gained should be explained in detail. Give background information.

At the end of surgical procedures, for patients who have had general anesthesia, an endotracheal tube (ETT) is removed ("extubation") from a patient's trachea during emergence from general anesthesia. Extubation can be performed either while the patient remains deeply anesthetized or, more commonly, when the patient has a return of protective airway reflexes. These reflexes include coughing as a result of the stimulation from the ETT on the glottis and the trachea. While it is common for coughing to occur, it is usually not dangerous and has minimal effect on surgical outcomes. However, there are certain surgical procedures where coughing can have a detrimental effect. Examples that have been reported included bleeding into the neck

following ear, nose, and throat surgery, which can cause compression of the trachea; and bleeding into the retina following ophthalmological procedures.

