Of all the different methods described in the literature, only the administration of remifentanyl, an ultra-short-acting opioid, showed any promise at decreasing the occurrence of coughing on emergence. All the published studies described using remifentanyl with a target-controlled-infusion (TCI) pump in order to achieve a specific concentration of the medication at its site of action ("effect site concentration"). In fact, most studies [1-6 and 8-9] recommend achieving a target effect site concentration from 1.5 to 2.5 ng/mL with varying levels of success achieved. Lee [1] identified that an effect site concentration of 2.14 ng/mL would have a 95% success at preventing coughing. A single study [7] described giving a bolus of remifentanyl but was unsuccessful at decreasing the incidence and frequency of coughing. These studies are not able to be replicated in the United States as TCI pumps are not cleared for use by the FDA. No modern TCI pump manufacturer has filed or is likely to file an application with the FDA, and hence the pumps are not available for use in the U.S.

Remifentanyl is particularly useful medication for this application given its safety profile and duration of action. Per the drug label information as submitted to the FDA, spontaneous respiration occurs at blood concentrations of 4 to 5 ng/mL in the absence of other anesthetic agents [10]. (This is twice the dose that will be administered in this study, and while other opioids may be prescribed with the potential to cause respiratory depression, in this study extubation will only occur once sufficient ventilation is demonstrated by the patient. Should respiratory depression or emergence from anesthesia cause more than 15 minutes of delay from the end of the case, the remifentanyl infusion will be stopped). In addition, recovery from anesthesia was rapid, predictable, and independent of the duration of the infusion [10] with a rapid elimination rate: the context-sensitive half-times is approximately 3 to 6 minutes. In the manufacturer clinical submission, no case of remifentanyl-induced delayed respiratory depression occurring more than 30 minutes after discontinuation of remifentanyl was found[10]. Finally, the addition of supplemental opiates for post-operative pain control did not delay recovery of respiratory drive in patients undergoing major surgery with remifentanyl-propofol total IV anesthesia [10].

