 - c. 2=moderate cough, strong and sudden contraction of the abdomen lasting for less than 5 seconds

Research Protections Office, [name], [contact]

d. 3=severe cough, strong and sudden contraction of the abdomen sustained for more than 5 seconds.

The above scoring will be assessed at the following four stages of extubation:

- a. eyes opening on verbal commands
 - b. tracheal cuff deflation
 - c. tracheal extubation
 - d. 1 min after extubation.
- 3) Extubation time: time between the termination of the anesthetic and extubation
 - 4) Time to recovery: time between extubation and the ability to perform purposeful movement (e.g. squeeze hand, thumbs up. Anesthesia providers ask patients to perform a purposeful movement as part of routine care.)
 - 5) Adverse events including hypoxemia despite oxygen supplementation and other respiratory complications such as laryngospasm, upper airway obstruction requiring intervention: bag mask ventilation, oral or nasal airway insertion.

Also documented will be the duration of the infusion and quantity of drug administered.

For research involving survey, questionnaires, etc.: Describe the setting and the mode of administering the instrument and the provisions for maintaining privacy and confidentiality. Include the duration, intervals of administration, and overall length of participation. (describe and attach all instruments)

Not applicable

Statistical Considerations: Delineate the precise outcomes to be measured and analyzed. Describe how these results will be measured and statistically analyzed. Delineate methods used to estimate the required number of subjects. Describe power calculations if the study involves comparisons. Perform this analysis on each of the primary and secondary objectives, if possible.

As this a comparative study, the measure outcomes described above will compared as follows:

- 1) The incidence of cough will be analyzed with a Fisher Exact Test
- 2) The coughing grade will be analyzed with a Mann-Whitney U test
- 3) Extubation time and time to recovery will be analyzed with an unpaired t-test, if appropriate
- 4) Adverse events will be categorized and then analyzed with a Fisher Exact Test

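### Secondary objective 3 is time to emergence, but the only interval that starts when the anesthetic is stopped ends at a discretionary extubation, whose timing the study drug can affect by routes other than return of consciousness.

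*Protocol*

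**What the plan says.** The third secondary objective (Protocol, Objectives) is "Measure the time to emergence from anesthesia". The outcomes that coordinators document (Protocol, Procedures) include two intervals, and neither is called time to emergence:

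- Item 3: "Extubation time: time between the termination of the anesthetic and extubation".
- Item 4: "Time to recovery: time between extubation and the ability to perform purposeful movement".

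Statistical Considerations plans an unpaired t-test, if appropriate, for each interval. It does not mention their sum.

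Three statements bear on when the tube comes out. The Purpose section says extubation is more commonly done "when the patient has a return of protective airway reflexes. These reflexes include coughing as a result of the stimulation from the ETT". The same section states that "extubation will only occur once sufficient ventilation is demonstrated by the patient". The Procedures section says only that "when clinically indicated the patient will be extubated". Patients who will be extubated while deeply anesthetized are excluded, so the analyzed patients are awake extubations.

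Cough is scored at four stages, the first of which is "eyes opening on verbal commands". The list of documented items does not include the time of that event. Sources of Materials says that event times are logged in the study spreadsheet, but not which events.

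**The concern.** Emergence is the patient's return of consciousness. Extubation is an act by the provider. Cues for that act include reflexes that the study drug is given to suppress and breathing that an opioid can slow. If either cue shifts between arms, extubation time can shift although patients wake equally fast, or a true difference in waking can be masked.

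Blinding does not remove this, because the provider responds to the cough or the breathing that is seen, not to knowledge of the arm.

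At stake is whether the trial can answer its third secondary objective cleanly. The protocol itself treats cough (objective 1), respiratory depression (objective 2) and emergence (objective 3) as separate questions. A measure for objective 3 that mixes all three cannot show which one moved.

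**Working it through.** **Which interval measures what.** Let A be the time the anesthetic is stopped, E extubation, M purposeful movement and W eye opening on command.

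- Item 3 = E − A
- Item 4 = M − E
- Item 3 + item 4 = M − A
- Not listed: W − A

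Suppose the extubation decision alone moves by δ minutes in one arm. Item 3 then changes by +δ and item 4 by −δ, while their sum is unchanged if M does not depend on E. The cancellation is only approximate: the infusion can end at extubation, so M may depend somewhat on E. Item 4 may also be zero or negative when movement comes before extubation. W − A does not contain E.

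**How large δ could be.** The protocol gives no standard deviation, expected difference or power for the time outcomes, so there is no figure to reproduce on this point. Two planning figures from Statistical Considerations are used below: cough rates of 70% and 30%, and 50 patients. The 50 reproduces as 25 per arm under a one-sided pooled two-proportion formula with 1:1 allocation. Here it serves only as the arm size.

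Assume emergence is identical in both arms and a coughing patient is extubated d minutes earlier than a non-coughing one. Then

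δ = (0.70 − 0.30) × d = 0.4 × d.

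That uses the overall cough incidence. Coughs at extubation and 1 minute after it, and probably those at cuff deflation, come after the decision and cannot have prompted it. If a share f of coughers in each arm cough before the decision, δ = 0.4 × f × d.

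| d (assumed, min) | f = 1 | f = 0.5 |
|---|---|---|
| 1 | 0.4 | 0.2 |
| 3 | 1.2 | 0.6 |
| 5 | 2.0 | 1.0 |

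The f = 1 column is the upper end when f is the same in both arms. It is not a strict bound, because f could differ by arm. The protocol gives neither f nor d.

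**What a shift would do to the t-test.** With 25 per arm, two-sided 0.05 and 48 degrees of freedom, the noncentrality is δ / (SD × √(2/25)). For δ = 1.2 and SD = 5 this is 1.2 / (5 × 0.283) = 0.85. The probability of declaring a difference when emergence is identical is:

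| δ (min) | SD 3 | SD 4 | SD 5 |
|---|---|---|---|
| 0 | 5% | 5% | 5% |
| 0.8 | 15% | 11% | 9% |
| 1.2 | 28% | 18% | 13% |
| 2.0 | 64% | 41% | 28% |

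The SDs are assumed. The table shows that a shift of a minute or two would matter, not that one will occur.

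**The case against.** Several points on the other side stand in whole or in part.

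- **Coughing is not an extubation criterion here.** A reader might infer that coughing triggers extubation, so that suppressing cough must move extubation time, and more so the better the drug works. The documents do not support this. The background text describes usual practice, the procedure leaves the moment to clinical judgement, and the one explicit condition, sufficient ventilation, does not require a cough. The shift is possible, not established.
- **A ventilation-driven delay is a real drug effect.** This stands. The Purpose section names respiratory depression and slow emergence as two causes of delay after surgery, and extubation time should capture both. The difficulty lies only in reading the result as emergence.
- **Items 3 and 4 together already reach purposeful movement.** This stands in part. The sum largely removes the problem, but the protocol tests only the components.
- **The time of eye opening may already be logged.** This is possible, since event times go into the spreadsheet, but the protocol does not say that this is one of them.
- **A statistical analysis plan can assign the measure to objective 3.** It can choose among recorded times. It cannot recover a time that was never recorded, and that part is settled by the protocol's list.

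**Conclusion.** The point holds as a weakness in how objective 3 is measured. No documented outcome is named as time to emergence. The nearest one ends at a discretionary act whose cues the study drug can affect. A difference in extubation time can therefore reflect the decision to extubate or respiratory drive rather than return of consciousness.

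It would go too far to say that extubation time carries no information on emergence, or that a bias of known size or sign is present. Neither can be derived from the protocol. The 0.4 × d figures rest on an assumed d, on identical emergence and on all coughs preceding the decision, so they are upper-end illustrations.

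This concerns a secondary outcome with no stated power, and the primary cough comparison is unaffected. It is a minor improvement, worth making because the remedy is cheap and an unrecorded time cannot be recovered later.

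**What to change.** 1. In the Procedures list of documented items, add the clock time of eye opening on verbal command, and name it among the event times logged in the spreadsheet.
2. In Statistical Considerations, name the time from anesthetic-off to eye opening as the measure for secondary objective 3. Optionally add anesthetic-off to purposeful movement as support, computed from the clock times so that movement before extubation causes no difficulty.
3. Keep extubation time as a separate process outcome, and do not report it as emergence.

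The cost is one extra time stamp, taken by a coordinator who already scores cough at that moment, and one extra line of analysis. Clinical care does not change. Eye opening still depends on when the command is given, so it is a more direct measure of emergence rather than a perfect one.
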